2.1. Study Design

This is a prospective, non-interventional (NI), multicentre study being conducted in Africa Middle East (AfME) countries. The aim is to understand palbociclib treatment patterns, clinical outcomes and QoL of patients with metastatic/locally advanced BC being treated in routine clinical practice in seven AfME countries: Egypt, Jordan, Lebanon, UAE, Qatar, Morocco and KSA.

Participation in this study is not intended to change the routine treatment patients receive, as determined by their prescribing physicians; all treatment decisions, type and timing of the disease monitoring are per routine clinical care, and at the discretion of the treating physician and patient.

Study population

[figure not shown]
Patients with HR+/HER2- metastatic/locally advanced BC within Egypt, Jordan, Lebanon, UAE, Qatar, Morocco and KSA will be enrolled from a geographically representative population as well as from diverse treatment settings (eg, academic and community sites). Patients whose treatment decision with palbociclib combination has been made by their treating physician and meet the eligibility criteria will be invited to participate in the study in a consecutive manner and over 12 months of recruitment.

Approximately 350-410 patients from 19 centers across the seven countries will be enrolled. The recruitment period (ie, from first patient in to last patient in) will span over 12 months.

Patients will be enrolled at the time of treatment initiation with palbociclib, and will be followed up over a maximum of 24-month period at time intervals per routine care, or until the end of Palbociclib treatment, progression or patients' withdrawal from the study (whichever comes first). Eligibility will be assessed at the date of the enrollment.

Prospective data on clinical characteristics, treatments patterns, clinical outcomes and QoL will be collected in accordance with routine standard of care visits (Figure 1). Data will be collected at enrollment (time of treatment initiation), during treatment with Palbociclib (at time intervals per routine care) and after treatment with palbociclib. After the end of treatment with palbociclib, data related to the first immediate subsequent treatment received will be collected.

Figure 1. Study Design

FPI: first patient in; LPI: last patient in; LPO: last patient out; QoL: quality of life

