8. RESEARCH METHODS

8.1. Study Design

This is a prospective, non-interventional (NI), multicenter study being conducted in Africa Middle East (AfME) countries. The aim is to understand palbociclib treatment patterns, clinical outcomes and QoL for patients with metastatic/locally advanced BC being treated in routine clinical practice in 7 AfME countries: Egypt, Jordan, KSA, Lebanon, Morocco, Qatar and UAE.

Approximately 200 patients from 19 centers across the 7 countries will be enrolled. The recruitment period (ie, from first patient into last patient in) will span over 18 months.

[figure not shown]
Patients will be enrolled at the time of treatment initiation with palbociclib and will be followed up over a 24-month period at time intervals per routine care, or until patient's withdrawal from the study or death (whichever comes first). Prospective data on clinical characteristics, treatment patterns, clinical outcomes and QoL will be collected ([Figure 1](#)).

Participation in this study is not intended to change the routine treatment patients receive, as determined by their prescribing physicians; all treatment decisions, type and timing of the disease monitoring are per routine clinical care, and at the discretion of treating physician and patient.

All assessments described in this protocol are performed as part of normal clinical practice or standard practice guidelines for the patient population and healthcare provider specialty in the countries where this non-interventional study is being conducted.

All assessments described in this protocol are performed as part of normal clinical practice or standard practice guidelines for the patient population and healthcare provider specialty in the countries where this non-interventional study is being conducted.

Figure 1. Study Design

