8.2. Setting

Patients with HR+/HER2- metastatic/locally advanced BC within Egypt, Jordan, KSA, Lebanon, Morocco, Qatar and UAE will be enrolled from a geographically representative population as well as from diverse treatment settings (eg, academic and community sites). Patients whose treatment decision with palbociclib combination has been made by their treating physician and meet the eligibility criteria will be invited to participate in the study in a consecutive manner and over 18 months of recruitment. Data will be collected in accordance with routine standard of care visits. Eligibility will be assessed at the date of the enrollment. Data will be collected at enrollment (time of treatment initiation), during treatment with palbociclib and after treatment with palbociclib, over a 24-month period (at time intervals per routine care). After the end of treatment with palbociclib, data related to the first immediate subsequent treatment received will be collected. Patients included in the study will be followed up until the end of the follow-up, withdrawal or death, whichever occurs first.

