1. Data is collected in accordance with normal standard of care visits; enter all data available per Data Entry Schedule into the electronic data capture system.
2. For a visit to be considered a follow-up visit, clinical outcomes data must be collected at minimum, in accordance with SOC.
3. Follow-up through End of Study: Enter data at SOC visits post palbociclib treatment.
4. BC treatment: including surgery, radiation, systemic chemotherapy, hormone therapy, and/or targeted therapy, in both neoadjuvant/adjuvant and metastatic disease settings, prior to, during and after palbociclib treatment; supportive care is also collected in the metastatic setting.
5. Data on the first immediate subsequent treatment used after the end of palbociclib treatment should be collected.
6. Clinical outcomes: overall clinical response as judged by treating physician, at intervals per standard of care schedule: progression free survival/time to progression, objective response rate, time to response and overall survival.
7. CBC: Baseline and during palbociclib treatment, enter any CBC during the 1st 3 cycles, then enter Day 1 (or prior to start of a new cycle) CBC for the subsequent cycles as per standard of care.
8. EORTC QLQ-C30 will be collected at baseline (before starting palbociclib) then every 3 months \pm 2 weeks after initiating treatment with palbociclib for the first year of treatment. After the first year of treatment with palbociclib, EORTC QLQ-C30 will be collected every 6 months \pm 4 weeks until the end of treatment with palbociclib.

PFIZER CONFIDENTIAL

CT24-WI-GL02-RF01 3.0 Non-Interventional Study Protocol Template For Primary Data Collection Study

02-Nov-2020

Page 19 of 41

090177e19bc3ff14\Approved\Approved On: 10-Nov-2022 09:28 (GMT)

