3. ANALYSIS SETS/POPULATIONS

3.1. Full Analysis Set

The Full Analysis Set will contain all patients who fulfil the eligibility criteria. Date of enrollment is the date of Palbociclib treatment initiation (baseline).

Censoring rules: The maximum follow-up of a patient is 24 months. Patients will be censored at the end of Palbociclib treatment, or if the treatment continues, at 24 months. Other censoring events before 24 months are patient's withdrawal, disease progression or death, whichever occurs first. Patients' subsequent treatments after Palbociclib treatment discontinuation /disease progression will be recorded. Patients who are lost to follow-up will be censored at their last visit. For some clinical outcomes, different censoring rules will be applied as described in [Section 6.1](#), [Section 6.2](#), and [Section 6.3](#).

Data collection is estimated to start in Q2 2021 and it will end in Q4 2024.

Table and Figure Shells are presented in [ANNEX 2](#).

Patient inclusion and exclusion criteria are explained in [Section 2.1](#). Summary of patient enrolment per country and study site will be described as shown in [Table Shell 1](#).

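### SAP 2.1 and 3.1 end follow-up and censor at end of palbociclib or progression, against the protocol's 24-month rule, which distorts the primary progression-free estimate and leaves some 1- and 2-year vital status uncounted

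*SAP*

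**What the plan says.** The two documents end follow-up at different points.

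- **Protocol 8.1:** patients are "followed up over a 24-month period at time intervals per routine care, or until patient's withdrawal from the study or death". Protocol 8.2 repeats it ("Patients included in the study will be followed up until the end of the follow-up, withdrawal or death, whichever occurs first") and has data collected "during treatment with palbociclib and after treatment with palbociclib, over a 24-month period". Neither section names progression or end of palbociclib as an end of follow-up.
- **SAP 2.1:** patients are "followed up over a maximum of 24-month period at time intervals per routine care, or until the end of Palbociclib treatment, progression" or withdrawal, whichever is first.
- **SAP 3.1:** "Patients will be censored at the end of Palbociclib treatment, or if the treatment continues, at 24 months". It adds: "Other censoring events before 24 months are patient's withdrawal, disease progression or death, whichever occurs first". It allows other rules for some outcomes in 6.1 to 6.3.
- **SAP 2.2.1:** the primary progression-free-and-alive proportion includes patients not censored under 3.1.
- **SAP 6.1:** this proportion is estimated by Kaplan-Meier, with no censoring rule given. The 1- and 2-year survival proportion is a crude ratio: patients alive over all who started treatment.
- **SAP 6.3:** time to progression (TTP) is explicitly censored at end of palbociclib. Exploratory PFS counts death as an event and is censored at the last record or the end of follow-up.
- **SAP Annex 1, Table 3:** the reasons for end of follow-up are death, withdrawal, loss to follow-up and completion of 24 months.
- **Data entry schedules (protocol Table 2, SAP Table 1):** the Clinical Outcomes row, which footnote 6 says includes progression and overall survival, is marked at baseline and during palbociclib but not after it. For the post-treatment period, footnote 5 says: "Data on the first immediate subsequent treatment used after the end of palbociclib treatment should be collected".

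**The concern.** Both primary objectives run from palbociclib initiation to fixed landmarks, whatever treatment the patient is then receiving. A rule that closes observation at progression or end of palbociclib cuts across both.

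For the progression-free proportion, an event listed as a censoring reason is not counted. Patients who stop without progression also leave the risk set at a time that may be related to their prognosis.

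For survival, the denominator is everyone who started, but vital status at the landmark may be unknown for anyone who progressed or stopped earlier, and the SAP does not say how to count them. Two analysts could follow the SAP and report very different 1-year figures.

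**Working it through.** The plan states no figure to reproduce, because the study is descriptive with no hypothesis test. The check compares the rules and then illustrates their effect.

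**1. Which rule governs the primary progression-free estimate?** SAP 2.2.1 points to 3.1. SAP 3.1 defers to 6.1 to 6.3 for exceptions, and 6.1 contains none, so 3.1 applies. If progression and death are both censoring events, no events remain and the Kaplan-Meier curve stays at 100%. That is unlikely to be intended, since 6.1 also defines when progression is recorded, but it is what 3.1 says.

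**2. Bias with progression and death restored as events, but censoring at end of palbociclib kept.** Let h be the progression hazard on treatment, c the hazard of stopping without progression, and k·h the hazard after stopping. Censoring at end of treatment estimates exp(−ht). The true proportion is

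exp(−(h+c)t) + ∫₀ᵗ c·exp(−(h+c)u)·exp(−kh(t−u)) du.

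h is set so that exp(−ht) equals the first-line PFS rates from a US chart review cited in protocol 6.1: 75.5% at 12 months and 51.6% at 18 months. The assumptions, which are not in the documents, are that 10% to 30% stop without progression by 12 months and that k runs from 1 to 3.

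| Month | k = 1 | 10% stop, k = 1.5 | 20% stop, k = 2 | 30% stop, k = 3 |
|---|---|---|---|---|
| 12 | 0 | +0.5 points | +2.0 points | +5.6 points |
| 18 | 0 | +1.1 points | +4.1 points | +10.2 points |

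For example, at 12 months with 20% stopping and k = 2 the true value is 73.5%, against 75.5% estimated.

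**3. Survival.** Patients alive after progression at a landmark number N × (OS − PFS). N = 200 is from protocol 8.1, and the OS and PFS rates are from the same cited chart review.

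- 12 months: 200 × (0.953 − 0.755) = 39.6, about 40. Known alive and progression-free: 200 × 0.755 = 151.
- 18 months: 200 × (0.925 − 0.516) = 81.8, about 82. Known alive and progression-free: 200 × 0.516 = 103.2, about 103.

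At 12 months, counting unknowns as not alive gives 75.5%. Counting them as alive gives a figure near 100%, because deaths after progression are then not seen. The cited value is 95.3%. Patients who stop palbociclib without progression would add to the unknowns and are not included here.

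**4. Share with a PFS event by 24 months**, assuming exponential times and using figures quoted in protocol 6.1:

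| Source figure | Formula | Share | Of 200 |
|---|---|---|---|
| 84.1% progression-free at 12 months (US, aromatase inhibitor) | 1 − 0.841² | 29% | 59 |
| 79.8% at 12 months (US, fulvestrant) | 1 − 0.798² | 36% | 73 |
| Median 24.8 months (letrozole trial) | 1 − 0.5^(24/24.8) | 49% | 98 |
| Median 9.5 months (fulvestrant trial) | 1 − 0.5^(24/9.5) | 83% | 165 |

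Each row treats the whole cohort as one treatment group, so the rows bracket an unknown mix. PFS events include deaths.

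**The case against.** The strongest reply is that the SAP text is wrong but the data will be there. Annex 1 omits progression and end of palbociclib from the reasons for ending follow-up, and it sources survival partly from the end-of-follow-up form at 1 and 2 years. SAP 2.1 itself has data collected after palbociclib. In the data entry schedules, footnote 3 calls for entries at post-treatment visits, and footnote 2 makes clinical outcomes the minimum content of a follow-up visit. Protocol 10.2 and 10.4.2 make a fatal outcome reportable through the end of the observation period. Protocol 7.1 also makes the survival objective conditional on available follow-up.

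Much of this stands. A reader might infer that 1- and 2-year survival cannot be ascertained at all. The documents do not support that: these routes exist, and patients still on treatment, or who died on it, are known. What remains is a conflict over when follow-up ends, an unmarked Clinical Outcomes cell, and no rule for unknown status. Safety reporting does not close the gap, because its period depends on the disputed observation period and Annex 1 does not list it as a source for survival.

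A reader might also infer that PFS in general is informatively censored. SAP 6.3 gives exploratory PFS its own rule, which does not name end of palbociclib, so that analysis is affected only if its end of follow-up is taken from SAP 2.1. Stopping observation at progression does no harm to PFS, since progression is the event.

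**Conclusion.** The contradiction is certain and reaches both primary analyses. It is not an authorised change: protocol 8.7 says major modifications to primary endpoint definitions or analyses would be reflected in a protocol amendment, and the amendment log shows none to follow-up.

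The sizes are conditional. The progression-free bias depends on stopping being related to prognosis. That is plausible, because the discontinuation reasons in Annex 1 include physical status and endocrine resistance, but it is not shown; the same caution applies to TTP. The survival figures are illustrations from a cited first-line cohort, whereas this study also enrols second-line patients.

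Two stronger statements should not be drawn. One is that survival will be reported near 100%, or alternatively capped at 51% or 17% at 2 years. These rest on opposite codings of unknown status, and the SAP states neither. The other is that 49% to 83% must have a PFS event by month 24. That uses trial medians only; the real-world rates in the protocol bring the lower end to about 29%. The claim that most deaths follow progression is not in the documents and is not needed.

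**What to change.** 1. In SAP 2.1 and 3.1, replace the follow-up and censoring text with the protocol rule: 24 months, withdrawal or death, regardless of palbociclib status.
2. For the primary progression-free proportion, state in SAP 6.1 that progression and death are events and that end of palbociclib is not a censoring point. Show end-of-treatment censoring only as a sensitivity analysis.
3. In SAP 6.1, estimate 1- and 2-year survival by Kaplan-Meier, censoring at the date last known alive. Changing the censoring date alone would do nothing while the crude ratio over all starters remains.
4. In protocol Table 2 and SAP Table 1, mark Clinical Outcomes in the post-treatment column (progression until documented, and vital status), consistent with footnotes 2 and 3.

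The cost is a SAP amendment, a small change to the schedule in both documents, and modest extra data entry at visits where sites already record subsequent treatment. Vital status that is not collected prospectively may be hard to recover later, so the schedule change is the more urgent part.

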2.1.1. Inclusion Criteria

Patients must meet all of the following inclusion criteria to be eligible for inclusion in the study:

1. *Age ≥ 18 years or older with diagnosis of adenocarcinoma of the breast with evidence of metastatic/locally advanced disease not amenable to treatment with curative intent.*
2. *Documented HR+ (ER+ and/or PR+) tumor based on local standards.*
3. *Documented HER2- tumor based on local standards.*
4. *Will initiate treatment with palbociclib plus letrozole/aromatase inhibitor or palbociclib plus fulvestrant in line with the licensed indication(s), as first or second line therapy for metastatic/locally advanced BC at enrollment.*
5. *Evidence of a personally signed and dated informed consent document indicating that the patient (or a legally acceptable representative) has been informed of all pertinent aspects of the study.*
6. *Patients who in the opinion of the investigator are willing and able to comply with regular clinic visits*

2.1.2. Exclusion Criteria

Patients meeting any of the following criteria will not be included in the study:

1. *Patients participating in any interventional clinical trial.*
2. *Patients on active treatment for malignancies other than metastatic/locally advanced BC at the time of enrollment.*
3. *Patients who are unable to understand the nature of the study and are unwilling to sign an informed consent.*

Data source

All data collected in this study are intended to capture the real-world treatment patterns and outcomes for patients with HR+/HER2- metastatic/locally advanced BC. An electronic case report form (eCRF) will be used for data collection. The eCRF must be signed by the investigator. The signature serves to attest that the information contained in the eCRF is true. At all times, the investigator has the final responsibility for the accuracy and authenticity of all clinical and laboratory data entered into the eCRFs.

Data for this study will be obtained via the sources outlined below.

2.1.3. Patient Medical Charts

The investigator or authorized medical staff will record clinical and treatment data from patients' existing medical records into an eCRF following each patient's standard of care clinic visit.

2.1.4. Patient Questionnaires and Quality of Life

All patients enrolled in the study will be asked to participate in completing the Quality of Life Questionnaire, EORTC QLQ-C30, to be collected at baseline (before starting palbociclib) then every 3 months ± 2 weeks after initiating treatment with palbociclib, for the first year of treatment, in accordance with routine standard of care visits. After the first year of treatment with palbociclib, EORTC QLQ-C30 will be collected every 6 months ± 4 weeks until the end of treatment with palbociclib, in accordance with routine standard of care visits.

Patients will complete these questionnaires on a paper form.

2.2. Study Objectives

With the introduction of palbociclib across different markets, this study aims to provide prospective, observational data of use of palbociclib in a real-world setting in terms of treatment patterns, clinical outcomes and QoL.

2.2.1. Primary Objectives

To determine clinical outcomes including (but not limited to):

- Proportion of patients who are progression free and alive at specific intervals (6, 12, 18 and 24 months). Patients who are not censored (see [Section 3.1](#)) at a certain time point will be included in the analysis.
- Proportion of patients alive after 1 and 2 years post palbociclib combination initiation.

2.2.2. Secondary Objectives

- To determine objective response rate (ORR).
- To describe the demographic and clinical characteristics of patients who have received palbociclib combination treatment in line with locally approved indications.
- To describe dosing and dose changes, interruptions, delays and discontinuations associated with palbociclib use in clinical practice.
- To describe supportive therapies received by patients while receiving palbociclib combination treatment.
- To summarize adjuvant therapies received for the treatment of early of locally advanced BC (Stages 0-IIIa).
- To describe treatments received in the advanced/metastatic setting, before and after palbociclib combination use.
- To assess QoL of patients receiving palbociclib combination treatment.

2.2.3. Exploratory Objectives

- To evaluate time to response (TTR), time to progression (TTP)/ PFS associated with palbociclib combination treatment – depending on availability of follow-up data.

09017760990673e30A5481150 PFIZER CONFIDENTIAL On: 28-Feb-2023 09:56 (GMT)

- *To describe the first immediate subsequent treatment used following end of treatment with palbociclib.*

3. ANALYSIS SETS/POPULATIONS

3.1. Full Analysis Set

The Full Analysis Set will contain all patients who fulfil the eligibility criteria. Date of enrollment is the date of Palbociclib treatment initiation (baseline).

Censoring rules: The maximum follow-up of a patient is 24 months. Patients will be censored at the end of Palbociclib treatment, or if the treatment continues, at 24 months. Other censoring events before 24 months are patient's withdrawal, disease progression or death, whichever occurs first. Patients' subsequent treatments after Palbociclib treatment discontinuation /disease progression will be recorded. Patients who are lost to follow-up will be censored at their last visit. For some clinical outcomes, different censoring rules will be applied as described in [Section 6.1](#), [Section 6.2](#), and [Section 6.3](#).

Data collection is estimated to start in Q2 2021 and it will end in Q4 2024.

Table and Figure Shells are presented in [ANNEX 2](#).

Patient inclusion and exclusion criteria are explained in [Section 2.1](#). Summary of patient enrolment per country and study site will be described as shown in [Table Shell 1](#).

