4.1. Primary Endpoints

This study focuses on the patients who have received Palbociclib treatment for BC. The primary endpoints that describe the primary objectives in the study population will be:

- The clinical outcomes of Palbociclib treatment patients (proportion of patients that are progression free and alive after certain time intervals post palbociclib combination initiation)

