6.1. Analysis for the Primary Objectives

Patients enrollment per country and site will be summarized as shown in [Table Shell 1](#).

For the primary objectives, clinical outcomes including the proportion of progression free and alive patients at different time intervals (6, 12, 18 and 24 months) and the proportion of patients who are alive 1 and 2 years post Palbociclib treatment initiation will be reported as shown in [Table Shell 2](#). The stratified tables will be presented as in Table Shells [3](#) - [9](#). The stratifications will be performed as described in [Section 3.2](#) by at least combination therapy and line of therapy.

The progression of the disease will be considered whenever the overall tumor response reported at any follow-up visit is progressive disease. The Kaplan-Meier (KM) method (product-limit method) will be used to estimate the proportion of subjects who are progression-free. The KM-estimate will be presented by 6 month intervals (6, 12, 18 and

24 months since the beginning of Palbociclib treatment) including the number of patients who were progression-free, those still at risk and the proportion of progression-free patients.

The proportion of the patients who are alive 1 and 2 years after Palbociclib treatment initiation will be calculated as the ratio of the number of patients who are alive 1 and 2 years over the number of patients who started the treatment (eligible patients).

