6.3. Analysis for the Exploratory Objectives

For the exploratory analyses, time to response (TTR), time to progression (TTP)/ progression free survival (PFS) will be studied and results will be presented as shown in [Table Shell 54](#). The stratified tables will be presented as in Table Shells [55-61](#).

TTR is defined as the length of time (in days) from the initiation of Palbociclib treatment until the first reported disease response (complete or partial).³⁴ Censoring rules presented in [Section 3.1](#) will be applied.

TTP is defined as the length of time (in days) from the initiation of Palbociclib treatment until the first reported disease progression.³⁴ Patients will be censored at the end of Palbociclib treatment, death, time of withdrawal, or end of the 24-month follow-up, whichever occurs first, at the respective time point. Specifically, death is not included in TTP but is considered as censoring event.

PFS is defined as the length of time (in days) from the initiation of Palbociclib treatment until the first reported disease progression or death due to any cause, whichever occurs first.³⁴ The disease progression will be considered at the first follow-up visit after the Palbociclib treatment initiation when the overall tumor response recorded is progressive disease. Patients with no disease progression documented will be censored at the last available medical record entry or end of the follow-up period. Patients who are lost to follow-up will be censored at their last visit.

Survival analyses will be used to estimate time to event endpoints TTR, TTP and PFS. The results of the survival analysis will be presented as the Kaplan-Meier survival curves and their 95% confidence intervals (CIs) that will be calculated using the log-log transformation of the survival probabilities.³⁶ Together with the Kaplan-Meier plots, the number of patients at risk at time intervals (eg, 90 days or as seen appropriate for the study) will be reported. [Figure Shells 1 and 2](#) show how time to response (TTR) and progression free survival (PFS) will be visualized as Kaplan-Meier plots including the number of patients at different time intervals. Kaplan-Meier plots can be presented by other categories (see [Section 3.2](#)), if enough data are available. Moreover, the results of the survival analysis will be reported as a descriptive summary table including the number of patients at risk, the number of patients

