Table Shell 54 - Descriptive summary table of the time to response, progression and progression free survival in Palbociclib treatment patients.

Variable	Summary statistics
Time to response (TTR)	
N at risk at the beginning	XX
N with event (response)	XX (xx%)
N censored	XX (xx%)
Q1 (95% CI)	xx.x (xx.x)
Median (95% CI)	xx.x (xx.x)
Q3 (95% CI)	xx.x (xx.x)
Min, max	XX.x, xx.,x
Missing	XX (xx%)
Time to progression (TTP)	
N at risk at the beginning	XX
N with event (disease progression)	XX (xx%)
N censored	XX (xx%)
Q1 (95% CI)	xx.x (xx.x)
Median (95% CI)	xx.x (xx.x)
Q3 (95% CI)	xx.x (xx.x)
Min, max	XX.x, xx.,x
Missing	XX (xx%)
Progression free survival (PFS)	
N at risk at the beginning	XX
N with event (disease progression)	XX (xx%)
N censored	XX (xx%)
Q1 (95% CI)	xx.x (xx.x)
Median (95% CI)	xx.x (xx.x)
Q3 (95% CI)	xx.x (xx.x)
Min, max	XX.x, xx.,x
Missing	XX (xx%)

Table Shell 55 - Descriptive summary table of the time to response, progression and progression free survival in Palbociclib treatment patients by treatment combination.

Variable	Combination therapy	
	Palbociclib plus letrozole/aromatase inhibitor	Palbociclib plus fulvestrant
Time to response (TTR)		
N at risk at the beginning	XX	XX
N with event (response)	XX (xx%)	XX (xx%)
N censored	XX (xx%)	XX (xx%)
Q1 (95% CI)	xx.x (xx.x)	xx.x (xx.x)
Median (95% CI)	xx.x (xx.x)	xx.x (xx.x)
Q3 (95% CI)	xx.x (xx.x)	xx.x (xx.x)
Min, max	XX.x, xx.,x	XX.x, xx.,x
Missing	XX (xx%)	XX (xx%)
Time to progression (TTP)		
N at risk at the beginning	XX	XX
N with event (disease progression)	XX (xx%)	XX (xx%)
N censored	XX (xx%)	XX (xx%)
Q1 (95% CI)	xx.x (xx.x)	xx.x (xx.x)
Median (95% CI)	xx.x (xx.x)	xx.x (xx.x)
Q3 (95% CI)	xx.x (xx.x)	xx.x (xx.x)
Min, max	XX.x, xx.,x	XX.x, xx.,x
Missing	XX (xx%)	XX (xx%)
Progression free survival (PFS)		
N at risk at the beginning	XX	XX
N with event (disease progression)	XX (xx%)	XX (xx%)
N censored	XX (xx%)	XX (xx%)
Q1 (95% CI)	xx.x (xx.x)	xx.x (xx.x)
Median (95% CI)	xx.x (xx.x)	xx.x (xx.x)
Q3 (95% CI)	xx.x (xx.x)	xx.x (xx.x)
Min, max	XX.x, xx.,x	XX.x, xx.,x
Missing	XX (xx%)	XX (xx%)

Table Shell 56 - Descriptive summary table of the time to response, progression and progression free survival in Palbociclib treatment patients by line of therapy.

Variable	Line of endocrine therapy	
	1 st	2 nd
Time to response (TTR)		
N at risk at the beginning	XX	XX
N with event (response)	XX (xx%)	XX (xx%)
N censored	XX (xx%)	XX (xx%)
Q1 (95% CI)	xx.x (xx.x)	xx.x (xx.x)

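### The SAP contradicts itself on death in the primary endpoint: patients must be progression free and alive, but the operative rules censor deaths, which can only raise the estimate or leave it unchanged

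*SAP*

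**What the plan says.** **The target.** SAP 2.2.1 sets the first primary objective as "Proportion of patients who are progression free and alive at specific intervals (6, 12, 18 and 24 months"). It adds that the patients included at each time point are those not yet censored under Section 3.1. SAP 4.1 repeats the target: "proportion of patients that are progression free and alive after certain time intervals post palbociclib combination initiation". Annex 1 (Table 3) defines the corresponding variable as patients who are alive with no progression reported, and names the end-of-follow-up form among its sources.

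**The censoring rule.** SAP 3.1 says: "Patients will be censored at the end of Palbociclib treatment, or if the treatment continues, at 24 months". It then lists further censoring events before 24 months: the patient's "withdrawal, disease progression or death, whichever occurs first". It allows exceptions: "For some clinical outcomes, different censoring rules will be applied as described in" Sections 6.1, 6.2 and 6.3.

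**The primary analysis.** SAP 6.1 opens with progression free and alive. It then recognises progression from a reported overall tumour response of progressive disease, and says the Kaplan-Meier method "will be used to estimate the proportion of subjects who are progression-free". It gives no rule for death in that analysis and no censoring rule of its own.

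**The exploratory analyses.** SAP 6.3 treats death as censoring for time to progression (TTP). It defines PFS to include death from any cause, then says: "Patients with no disease progression documented will be censored at the last available medical record entry or end of the follow-up period". In Table Shell 54 the PFS block carries the same label as the TTP block, "N with event (disease progression").

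**The concern.** Under the stated target, a patient who dies without documented progression has failed. Censoring that patient treats their later course as unknown but like that of patients still under observation. The curve then estimates time to progression with deaths set aside, which is a different quantity from the one named in the objective.

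The headline proportions at all four time points are at stake. Two careful programmers could also reach different primary results from the same data, one following 3.1 with 6.1 and the other following Annex 1. A larger sample would not reduce the discrepancy.

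**Working it through.** **Step 1: the rules side by side.**

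| Source | Event | Death without progression |
|---|---|---|
| 2.2.1, 4.1, Annex 1 (target) | loss of progression-free-and-alive status | failure |
| 3.1 read alone | none (progression is also listed) | censored |
| 3.1 with 6.1 | reported progressive disease | censored; 6.1 gives no exception |
| 6.3 TTP | reported progression | censored, stated explicitly |
| 6.3 PFS definition | progression or death | event |

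The third row is the operative primary analysis. Its event and its handling of death match the TTP row. The second row cannot be intended, because with no events the Kaplan-Meier estimate stays at 100%.

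**Step 2: direction.** At a death time with n patients at risk, the Kaplan-Meier product gains a factor (1 − 1/n) if death is an event and a factor of 1 if it is censored. The risk sets are the same either way. Censoring deaths can therefore only raise the estimate or leave it unchanged. This needs no assumption.

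**Step 3: illustrative size.** The SAP states no expected value for this endpoint, so there is no planned figure to reproduce. Inputs come from Protocol 6.1:
- First-line palbociclib plus letrozole, US chart review: PFS 75.5% and survival 95.3% at 12 months; PFS 51.6% and survival 92.5% at 18 months.
- US subgroup of the multinational chart review, 12 months: progression free 84.1% and survival 95.1% with an aromatase inhibitor (AI); 79.8% and 87.9% with fulvestrant.

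Let S be the progression-free-and-alive proportion, D = 1 − survival, and f the share of deaths without documented progression. The documents do not give f, so it is varied from 0 to 1. With constant cause-specific hazards, the death-censored Kaplan-Meier estimates

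S^(1 − r), where r = f × D / (1 − S).

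At f = 1:
- Letrozole, 12 months: r = 0.047/0.245 = 0.192; 0.755^0.808 = 0.797.
- Letrozole, 18 months: r = 0.075/0.484 = 0.155; 0.516^0.845 = 0.572.
- AI, 12 months: r = 0.049/0.159 = 0.308; 0.841^0.692 = 0.887.
- Fulvestrant, 12 months: r = 0.121/0.202 = 0.599; 0.798^0.401 = 0.913.

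| Cited rates | f = 0 | f = 25% | f = 50% | f = 100% |
|---|---|---|---|---|
| Letrozole, 12 months | 75.5% | 76.5% (+1.0) | 77.6% (+2.1) | 79.7% (+4.2) |
| Letrozole, 18 months | 51.6% | 52.9% (+1.3) | 54.3% (+2.7) | 57.2% (+5.6) |
| AI, 12 months | 84.1% | 85.2% (+1.1) | 86.4% (+2.3) | 88.7% (+4.6) |
| Fulvestrant, 12 months | 79.8% | 82.5% (+2.7) | 85.4% (+5.6) | 91.3% (+11.5) |

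A simulation with 200 patients and 2,000 runs agrees. At f = 1 and 12 months, the letrozole rates gave 79.7% with deaths censored against 75.5% with deaths counted. The fulvestrant rates gave 91.4% against 79.8%.

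**Step 4: scale.** With the current target of about 200 patients, the 95% half-width at 75.5% is 1.96 × √(0.755 × 0.245 / 200) = 6.0 points.

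**The case against.** The strongest reply is that the SAP already says the right thing. Annex 1 requires patients to be alive, 2.2.1, 4.1 and the opening of 6.1 say so too, and 6.3 shows that the authors know how PFS differs from TTP. On this view the list in 3.1 is a loosely worded account of when observation ends, since it names progression as well as death and nobody would censor progression here. This stands in part: it shows the fault is a contradiction rather than a settled choice to censor deaths. It does not remove the fault. 3.1 promises exceptions in 6.1, 6.1 supplies none for death, and 2.2.1 sends the analyst back to 3.1.

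The size is also open to challenge, and this stands:
- f has no source in the documents and could be zero.
- Progression can be recorded on the clinician's judgement without a scan, which would lower f.
- 3.1 already censors at the end of palbociclib, so later deaths do not enter by this route, although the formula uses all deaths.
- The protocol calls the US subgroup figures progression-free rates and does not say whether they count deaths.
- Fulvestrant is the most extreme of the four examples.

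A reader might infer from the loose 6.3 sentence and the shell label that PFS and TTP become the same quantity and that exploratory PFS is biased too. The documents do not support that. 6.3 and Annex 1 both include death in PFS, and the censoring times differ: TTP stops at the end of palbociclib, PFS at the last record or end of follow-up. The 6.3 sentence most naturally means patients without an event. The progression-only label is visible in Shells 54-57 and 61; Shells 58-60 cannot be read in the available text.

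**Conclusion.** The point holds as a contradiction in the definition of the primary event. On the operative text of 3.1 and 6.1, deaths without documented progression are censored, and the primary estimate is too high or unchanged. The direction is certain under that reading; the size is not. The illustrations run from zero to 4.2 points (12 months) and 5.6 points (18 months) for first-line letrozole, and to about 11.5 points for fulvestrant. They assume constant cause-specific hazards, that the cited rates count deaths as events, and a freely varied f. At f = 25% the letrozole bias is only 1.0 to 1.3 points, well inside the sampling error.

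A reader might go further and conclude that the primary result will be overstated by a known amount, or that the 1- and 2-year proportions alive are affected. Neither follows. The documents do not fix f, and 6.1 computes the proportions alive as a crude ratio over all patients who started treatment. Censoring at the end of treatment is a separate question and plays no part in these figures.

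**What to change.** 1. In SAP 6.1, state that the event in the primary Kaplan-Meier analysis is the earlier of first documented progressive disease and death from any cause, in line with Annex 1 and the PFS definition in 6.3.
2. In SAP 3.1, state that progression and death are events, not censoring, for this endpoint and for PFS.
3. For consistency, limit the 6.3 PFS censoring sentence to patients who are alive, and relabel the PFS event row in the shells (54-57 and 61, and 58-60 if they match) as progression or death.

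The cost is SAP wording and shell labels. Death is already a recorded reason for end of follow-up, and Annex 1 already lists that form as a source for the primary variable. The change restores the endpoint stated in Protocol 7.1. Estimates may come out somewhat lower. No change to the proportion-alive analysis or to the end-of-treatment censoring time is part of this point.
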